8.4.1. Blinding

Both the investigator and the volunteer will be blinded to the study drug/placebo but not to the group assignment as it is a dose escalation trial. The syringes containing the study drug/placebo will be covered by the study pharmacist to insure blinding of the study.

8.4.2. Blinding and Code Breaking Procedures

Dose labels will not allow for identification of treatment. The investigator and volunteer will not know which treatment is administered. The pharmacist responsible for product preparation will prepare the appropriate product

for the volunteer as indicated by the block randomization and cover the syringe to prevent identification. The nurse/physician responsible for injection and the volunteer will not know which product is injected as the syringes will be blinded (a film will be affixed on each syringe by the staff responsible for product preparation).

Consequently, two sealed envelopes for each volunteer containing emergency decoding information for each volunteer will be issued by the research pharmacist. The emergency decoding information indicates the treatment corresponding to each randomization number. One envelope will be retained by the investigator and the other one by the research pharmacy/medical monitor.

The code can be broken by opening the individual envelope for the volunteer. The vaccine/diluent injected will be indicated in the envelope. The code may be broken only in case of a Serious Adverse Event and if identification of the treatment can influence the treatment of the adverse event.

In case of code breaking, the name of the person who requests it, the date and reason must be written on the list. The event must be immediately reported on the CRF. The sponsor will immediately be informed by phone or by fax.

At the end of the trial the emergency decoding information will be returned to the sponsor and checked. In the absence of any problem, codes will be broken at the time of the analysis, when the data base is validated and locked.

[figure not shown]
8.5. Identification of participants as volunteers in HIV vaccine trial

All volunteers will receive an individual identification card indicating their status as an HIV-1 vaccine trial participant. All volunteers will be counseled periodically regarding the potential for testing positive on routine screening tests for HIV-1 as a consequence of participation in this trial and receiving these vaccine products. All volunteers will be offered further confirmatory testing and certification as to the nature of their vaccine trial participation whenever needed to address complications arising at home, at work or in the community that could arise from routine screening from HIV-1.

8.6. Detection of inter-current HIV-1 infections.

Each volunteer will be counseled at each visit and an algorithm followed to identify inter-current HIV-1 infections. The algorithm is shown in [Figure 1](#) and uses FDA approved serological and nucleic acid diagnostic kits at each step. If an individual is determined to have an inter-current infection with HIV-1 they will be excluded from further immunizations and counseled about their medical options. Enrollment in the trials does not include subsequent care for an inter-current HIV-1 infection. The volunteer will be counseled on how to access that care if they choose to do so.

Figure 1: Algorithm to detect inter-current HIV-1 infections

[figure not shown]
9. STUDY DRUG MATERIALS AND MANAGEMENT

9.1. Study Drug

The FLSC final product consists of 0.3 mg/ml of purified FLSC Drug Substance formulated with Aluminum Phosphate (AlPO₄) at 2.4 mg/mL in binding buffer (mannitol 40 mg/mL; sodium acetate 5 mM, pH 6.2. Aluminum ion concentration is 1.2 mg/mL and 1.3 mL product is vialled in 2cc glass vials.

9.2. Study Drug Packaging and Labeling

The information to appear on each study medication vial label will be:

The placebo will be preservative free saline provided by the IHV research pharmacy.

9.3. Study Drug Storage

FLSC will be stored between +2°C and +8°C as directed by the manufacturer.

9.4. Study Drug Preparation

The product preparation and the injection will be performed in different places. The product preparation must be performed in the absence of the investigator and of the nurse responsible for injection. This will be performed by a pharmacist or nurse. If it is a nurse, the nurse must not be performing other duties with the study.

9.4.1. FLSC 75 ug (Group 1)

Before injection, the FLSC vial will be removed from the refrigerator and swirled until a uniform solution results. Once the FLSC is in a uniform solution, 0.25 ml (75ug) of FLSC will be withdrawn from the vial using a 22-25 gauge, 25 mm (1 inch) needle with a 1-mL sterile disposable syringe. The syringe will then be covered with a film/aluminum foil to prevent visualization of the product.

9.4.2. FLSC 150 ug (Group 2)

Before injection, the FLSC vial will be removed from the refrigerator and swirled until a uniform solution results. Once the FLSC is in a uniform solution, 0.5 ml (150ug) of FLSC will be withdrawn from the vial using a 22-25 gauge, 25 mm (1 inch) needle with a 1-mL sterile disposable syringe. The syringe will then be covered with a film/aluminum foil to prevent visualization of the product.

9.4.3. FLSC 300 ug (Group 3)

Before injection, the FLSC vial will be removed from the refrigerator and swirled until a uniform solution results. Once the FLSC is in a uniform solution, 1.0 ml (300ug) of FLSC will be withdrawn from the vial using a 22-25 gauge, 25 mm (1 inch) needle with a 1-mL sterile disposable syringe. The syringe will then be covered with a film/aluminum foil to prevent visualization of the product.

9.4.4. Placebo (Groups 1-3)

Before injection, depending on the group (see [Table 7](#)), the saline will be withdrawn using a 22-25 gauge, 25 mm (1 inch) needle with a 1-mL sterile disposable syringe. The syringe will then be covered with a film/aluminum foil to prevent visualization of the product.

Table 7: Placebo Groups

Group Number	Volume of Saline
1	0.25 ml
2	0.5 ml
3	1.0 ml

9.5. Administration

Immunizations will be administered on an outpatient basis on Day 0, Day 28, Day 56, and Day 168. Evaluations listed on the study schema will be conducted prior to immunization with the study vaccine. Total time required in the clinic for an immunization visit will be approximately one hour, unless the subject experiences an Adverse Event which requires additional treatment. The volunteer will be instructed to call a designated staff member immediately if an Adverse Event should occur after the volunteer leaves the clinic.

The intramuscular route will be used in all cases. At all stages of the preparation, aseptic procedures must be followed. After cleansing the site of injection with a suitable antiseptic, the injections will be given as an intramuscular injection in the deltoid muscle of the volunteer's non-dominant arm (unless preferred otherwise by the patient) with a 22 gauge 25 mm (1 inch) needle. All of the product contained in the syringe will be injected. As noted in [Section 9.4](#), according to the group number, drug product or diluent will be given as an intramuscular injection in the deltoid muscle of the volunteer's non-dominant arm per institutional protocol. The study vaccine may be given in the deltoid muscle of the dominant arm at the investigator's discretion (e.g., open wound near/on the proposed injection site, request of the volunteer, etc.). Immediately after injection, the subject will be observed closely for 30 minutes. Complete vital signs will be recorded prior to administration, at 15 minutes and 30 minutes post-injection. Injection site evaluations will be recorded at 15 minutes and 30 minutes post-injection. The volunteer will be instructed in the evaluation of these local reactions; study personnel will observe and instruct while the volunteer takes his/her own temperature at Visit 1 (as guide for subsequent evaluations. Volunteer diary card for immunization reactions will be dispensed and instructions for its completion will be given.

If there are no clinically meaningful abnormalities and the volunteer has no complaints which are considered cause for concern by the Principal Investigators or his designee, he/she may leave the clinic with instructions to immediately call a designated staff member should any complications arise. If there are any local or systemic reactions present, the volunteer will be asked to return to the clinic the following day for a follow-up visit.

Treatment of AEs will be at the discretion of the Investigator and the clinic staff. Medication (epinephrine and Benadryl) and equipment for treatment of emergencies will be available during injection and for 30 minutes immediately following to allow a rapid response to any acute reactions. At all stages of the administration, aseptic procedures must be followed. It is important to use a separate sterile syringe for each individual study participant to prevent transmission of infectious agents. Once taken out of the refrigerator, prepare as soon as products have reach room temperature, and once reconstituted, use as soon as possible, but within 1 hour. Discard reconstituted unused vaccine.

After reconstitution and preparation, inspect the vaccine for particulate matter and discoloration. If either of these conditions exist, the vaccine should not be administered and another syringe/replacement dose should be selected. The staff in charge of product preparation will affix an opaque cover on each syringe.

9.6. Study Drug Accountability

The IHV Research pharmacy will be responsible for study drug accountability. The Research Pharmacist will utilize the University of Maryland Medical Center Policy 06-05, Investigational Drug Accountability to ensure complete and accurate records of investigational drug accountability. (See [Appendix 3](#))

9.7. Study Drug Handling and Disposal

All vaccine products will be prepared by an investigational pharmacist who will provide the product to research study personnel in a blinded fashion in a syringe pre-packaged and prepared with vaccine antigen and diluent, vaccine antigen and adjuvant, or placebo (diluent) and diluent mixed together. All materials for this study must be stored under recommended storage conditions in an area free of environmental extremes with controlled limited access. The FLSC will be kept at +2°C to +8° Celsius; and brought out to room temperature no earlier than one hour prior to administration of vaccine. The placebo (preservative free normal saline) will be stored as per package insert.

10. CLINICAL SAMPLE COLLECTION

10.1. Blood Sample Collection

Blood sample collection will occur as outlined in [Table 4](#) and in [Section 6.1.1](#). Blood volumes for these assessments will be as outlined in [Table 5](#).

10.2. Urine Sample Collection

Urine sample collection will occur as outlined in [Table 4](#) and in [Section 6.1.1](#).

10.3. Sample Analysis

All safety laboratory assessments will be analyzed by the University of Maryland Medical Center Clinical Laboratory as noted in [Section 15.2](#)

All immunogenicity laboratory assessments will be analyzed at one of the laboratories outlined in [Section 15.2](#) and per description in [Section 12.2](#) and [Section 15.3](#).

11. ASSESSMENT OF SAFETY

Although no safety concerns have been identified with this vaccine product in animal studies to date, there is a theoretical risk of the development of anti-CD4 antibodies. Antibodies against CD4 have been shown to occur in HIV infected individuals and their significance is not known. However, the presence of these antibodies has not been demonstrated to be deleterious in these individuals. Therefore, we do not believe that this vaccine poses a risk to the individuals enrolling in the trial. In order to ensure volunteer safety, we are monitoring CD4 cell count frequently throughout the trial. Any individual who experiences any of the criteria noted in [Section 7.3.1](#) will be withdrawn from the study.

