3. Follow-up Phone contact by study nurse (24-48 hours after first immunization)

- a. Obtain interim history including: local and systemic reactions, post-injection oral temperature, Adverse Events, and concomitant medication.

4. **Study Visit 2, Day 14 (Week 2): Follow-up Clinical Visit**
 - a. Obtain interim medical history including: review of volunteer diary, adverse events, concomitant medications, and safety labs.
 - b. Perform exam of previous injection site and directed physical examination as indicated, including vital signs and temperature.
 - c. Counsel volunteer regarding avoiding HIV risk behaviors
 - d. Collect blood for safety labs and immunologic studies ([Table 4](#), [Table 5](#) and [Section 11](#)).
5. **Study Visit 3, Day 28 (Week 4): Second Immunization**
 - a. Obtain interim medical history including: adverse events, concomitant medications, and safety labs.
 - b. Perform exam of previous injection site and directed physical examination as indicated, including vital signs and temperature.
 - c. Conduct urine pregnancy test (female volunteers).
 - d. Collect blood for safety labs ([Table 4](#), [Table 5](#) and [Section 11](#)).
 - e. Collect blood for immunologic studies ([Table 4](#) and [Table 5](#) and [Section 12](#)).
 - f. Administer second injection of the study vaccine as an intramuscular injection in the deltoid muscle as per [Section 9.5](#).
 - g. Record vital signs and examine injection site for local reactions at 15 and 30 minutes post-injection.
 - h. Observe and instruct while volunteer takes own temperature and assesses local reactions (as a guide for subsequent evaluations at home).
 - i. Counsel volunteer regarding avoiding HIV risk behaviors
 - j. Dispense diary for immunization reactions ([Appendix 1](#)). Give instructions for its completion and for digital thermometer use.
6. **Follow-up Phone contact by study nurse (24-48 hours after second immunization)**
 - a. Obtain interim history including: local and systemic reactions, post-injection oral temperature, Adverse Events, and concomitant medication.
7. **Study Visit 4, Day 42 (Week 6): Follow-up Clinical Visit**
 - a. Obtain interim medical history including: review of volunteer diary, adverse events, concomitant medications, and safety labs.
 - b. Perform exam of previous injection site and directed physical examination as indicated, including vital signs and temperature.
 - c. Counsel volunteer regarding avoiding HIV risk behaviors

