6.4. Dose Escalation Criteria

Requirements to begin immunizations in the higher dose groups (Groups 2 and 3) are listed below.

1. Safety data including the visit 4 data (2 weeks after the second immunization) in the 20 volunteers in the lower dose group has been collated and then reviewed by the DSMB.
2. DSMB review is completed, no safety concerns are noted, and approval to enroll the next group is granted.

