6.4.1. Safety Criteria for Adjustment or Stopping Doses

1. If more than 5 volunteers in any group have an unexplained CD4 cell count decline (confirmed by assays at least 4 weeks apart) of greater than 30 percent and corroborated by a similar CD4% decline (>30%), immunizations in that study group will be stopped. No further immunizations will be allowed until after all data are reviewed by the IHV DSMB and the DSMB authorizes immunizations to continue in this group. Follow-up visits for safety will continue during this time. Note that an unexplained drop in CD4 cell count is defined as a decline that cannot be explained by an intercurrent illness or other event known to cause decreased CD4 cell counts.
2. The entire study will be stopped if five or more vaccine related severe (grade 3 or 4) adverse events occur in any group.
3. The volunteer will have immunizations stopped upon the occurrence of an unexpected Grade IV event felt by the investigator to be related to the study vaccine. No further immunizations will be allowed until after all data are reviewed by the IHV DSMB and the DSMB authorizes immunizations to continue in this group. Follow-up visits for safety will continue during this time.
4. The entire study immunizations will be stopped upon the occurrence of one unexpected serious adverse event felt to be related to the study vaccine.

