7.3.1.1. Conditions mandating withdrawal from the Study

Individual volunteers will be withdrawn from further immunizations on the study for the following reasons:

- Experiencing a grade 4 toxicity/adverse event or serious adverse event considered by the principal investigator to be related to study vaccine
- Becoming pregnant during the study
- Requiring cytotoxic chemotherapy or immunomodulatory therapy during the course of the study
- Missing 2 immunization visits (injections)

Note that those withdrawn for toxicity reasons will continue to be followed for safety as described in [Section 6.1.1.7](#).

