7.3.3. Reasons to Halt Study

If 5 or more volunteers in any group have an unexplained CD4 cell count decline (confirmed by assays at least 4 weeks apart) of greater than 30 percent and corroborated by a similar CD4% decline (>30%), immunizations in that study group will be stopped. No further immunizations will be allowed until after all data are reviewed by the IHV DSMB and the DSMB authorizes immunizations to continue in this group. Follow-up visits for safety will continue during this time. Note that an unexplained drop in CD4 cell count is defined as a decline that cannot be explained by an intercurrent illness or other event known to cause decreased in CD4 cell counts. Other reasons are noted in [Section 6.4.1](#) and [Section 6.5](#).

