11.5. Reporting Adverse Events

11.5.1. Adverse Events

All adverse events, including both observed and volunteered problems, complaints, signs or symptoms, and any death occurring while on study are to be recorded (whether or not the event is related to vaccine administration). The duration and intensity of the event as well as whether or not the event might be associated with the study medication or other causes will be evaluated.

The severity of each adverse event will be graded according to the common toxicity criteria of the AIDS Clinical Trials Group (ACTG) as listed in [Appendix 2](#). When intensity changes occur more frequently than once a day, the maximum severity for the event should be listed. If the intensity category changes over a number of days, then these changes should be recorded separately, having distinct onset and stop dates for each grade.

If the investigator has evidence that the adverse event is not caused by the vaccine, and after consultation with the study Principal Investigator, then the study vaccine may be continued. All adverse events, irrespective of causality, must be recorded in the CRF. All changes in study regimen must be accurately recorded on the study drug pages of the CRF. All adverse events occurring during the trial must be evaluated by the investigator and graded according to the adverse experience grading table ([Appendix 2](#)). **Any serious adverse event (including death) due to any cause must be reported immediately to the principal investigator and the sponsor.** The decision to remove a patient for an adverse event, whether laboratory or clinical, will depend on the severity of the event and its relation to the vaccine and study requirements and therefore, will require judgment. The guiding principal will be to insure the safety of participants and integrity of the study. It is expected that all vaccine related grade 4 events will require discontinuation as will most grade 3 events. Vaccines will be discontinued for any Grade event or at the discretion of the investigator or wish of the volunteer. If a volunteer is withdrawn due to an adverse event follow-up will be conducted as outlined in [Section 6.1.1.7](#).

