APPENDIX 2. TABLE FOR GRADING SEVERITY OF ADULT ADVERSE EXPERIENCES

(Adapted from the ACTG and AVEG tables)

ABBREVIATIONS: Abbreviations utilized in the Table:

ULN = Upper Limit of Normal	LLN = Lower Limit of Normal
Rx = Therapy	Req = Required
Mod = Moderate	IV = Intravenous
ADL = Activities of Daily Living	Dec = Decreased

ESTIMATING SEVERITY GRADE

For abnormalities NOT found elsewhere on the Table, use the scale below to estimate grade of severity:

GRADE 1 Mild	Transient or mild discomfort; no limitation in activity; no medical intervention/therapy required
GRADE 2 Moderate	Mild to moderate limitation in activity - some assistance may be needed; no or minimal medical intervention/therapy required
GRADE 3 Severe	Marked limitation in activity, some assistance usually required; medical intervention/therapy required, hospitalizations possible
GRADE 4 Life-threatening	Extreme limitation in activity, significant assistance required; significant medical intervention/therapy required, hospitalization or hospice care probable

SERIOUS OR LIFE-THREATENING AEs

ANY clinical event deemed by the clinician to be serious or life-threatening should be considered a grade 4 adverse experience. Clinical events considered to be serious or life-threatening include, but are not limited to:

seizures, coma, tetany, diabetic ketoacidosis, disseminated intravascular coagulation, diffuse petechiae, paralysis, acute psychosis

MISCELLANEOUS

- > When two values are used to define the criteria for each parameter, the lowest values will occur first.
- > Parameters are generally grouped by body system.
- > Some protocols may have additional protocol specific grading criteria.

PARAMETER	GRADE 1 MILD	GRADE 2 MODERATE	GRADE 3 SEVERE	GRADE 4 POTENTIALLY LIFE THREATENING
HEMATOLOGY				
Hemoglobin	8.0 g/dL - 9.4 g/dL	7.0 g/dL - 7.9 g/dL	6.5 g/dL - 6.9 g/dL	<6.5 g/dL
Absolute Neutrophil Count	1000 - 1500/mm ³	750 - 999/mm ³	500 - 749/mm ³	<500/mm ³
Platelets	75,000 - 99,000/mm ³	50,000 - 74,999/mm ³	20,000 - 49,999/mm ³	<20,000/mm ³
Prothrombin Time (PT)	>1.0 - 1.25 x ULN	>1.25 - 1.5 x ULN	>1.5 - 3.0 x ULN	>3 x ULN
PTT	>1.0 - 1.66 x ULN ULN	>1.66 - 2.33 x ULN	>2.33 - 3.0 x ULN	>3.0 x ULN
Methemoglobin	5.0 - 10.0%	10.1 - 15.0%	15.1 - 20.0%	>20%
CHEMISTRIES				
SODIUM				
Hyponatremia	130 - 135 meq/L	123 - 129 meq/L	116 - 122 meq/L	<116 meq/L
Hypernatremia	146 - 150 meq/L	151 - 157 meq/L	158 - 165 meq/L	>165 meq/L
POTASSIUM				

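### CD4 counts are named as the volunteer safeguard, but the only on-study CD4 thresholds stop a whole group; stopping one volunteer's injections for a CD4 fall is left to judgment

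*Combined protocol and SAP*

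**What the plan says.** **The safeguard.** Section 11 raises the theoretical risk of anti-CD4 antibodies and answers it with "In order to ensure volunteer safety, we are monitoring CD4 cell count frequently throughout the trial". It then says that anyone meeting a 7.3.1 criterion will be withdrawn.

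**Individual rules.** Section 7.3.1.1 lists four mandatory conditions. The first is "Experiencing a grade 4 toxicity/adverse event or serious adverse event considered by the principal investigator to be related to study vaccine". The others are pregnancy, chemotherapy or immunomodulatory therapy, and two missed immunization visits. Section 7.3.1.2 lists conditions that permit withdrawal and names no CD4 value. Section 6.4.1 item 3 stops a volunteer for an unexpected, related Grade IV event.

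**Group rules.** Section 7.3.3 begins "If 5 or more volunteers in any group have an unexplained CD4 cell count decline (confirmed by assays at least 4 weeks apart" and requires a fall above 30% in count with a similar fall in CD4%. Section 6.4.1 item 1 uses the same definition but needs more than five volunteers. The action in both is at group level: "immunizations in that study group will be stopped".

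**Grading and removal.** Appendix 2 has no CD4 or lymphocyte row. Section 11.1.5 allows suitable other criteria where the table does not apply. Section 11.5.1 says that removal for an adverse event, "laboratory or clinical, will depend on the severity of the event and its relation to the vaccine and study requirements and therefore, will require judgment".

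**Review points.** The second, third and fourth injection visits in 6.1.1.3 include this step: "Obtain interim medical history including: adverse events, concomitant medications, and safety labs". Section 6.4 requires DSMB review of "Safety data including the visit 4 data (2 weeks after the second immunization) in the 20 volunteers in the lower dose group" before the next group starts.

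**The concern.** Section 4.5.2 says that the risk of auto-anti-CD4 antibodies shapes the design of the phase 1 safety work, and 6.2 says that the vaccine's safety has not previously been evaluated in humans. The same sections are also reassuring: no autoimmune response to CD4 was seen in the macaque study, and the CD4 part is expected to be poorly immunogenic in people.

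Given that emphasis, one would expect the section that Section 11 points to for individual action to contain a CD4 trigger. It does not. CD4 is measured at every scheduled clinic visit and the result is available for review, but no CD4 value is tied to an action for the person it belongs to. A healthy volunteer with a confirmed fall above 30% can receive another injection without breaching any CD4 criterion, and two volunteers with the same fall can be handled differently.

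**Working it through.** The plan states no figure on this point, so the check is mainly a comparison of text, with simple counts.

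**1. Where CD4 appears as a criterion**

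| Section | CD4 value? | Acts on |
|---|---|---|
| 7.1 item 9 | normal range | entry only |
| 6.4.1 item 1 | >30% fall, more than 5 volunteers | group |
| 7.3.3 | >30% fall, 5 or more volunteers | group |
| 6.4.1 item 3 | none | individual |
| 7.3.1.1 | none | individual |
| 7.3.1.2 | none | individual, permissive |
| 11.5.1 | none | individual, judgment |
| 11.6 (DSMB) | none | any, judgment |

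No row joins an on-study CD4 value to an individual action.

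**2. How many cases fit below the group rule.** Table 3 gives 15 vaccine and 5 placebo volunteers per group. The stricter rule, 7.3.3, acts at 5, so 5 − 1 = 4 cases can exist without it acting. 4/20 = 20%; if all four are vaccinees, 4/15 = 27%. Under 6.4.1 item 1 alone the number would be 5.

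**3. Whether group-rule confirmation could guide injections.** Confirmation needs assays at least 28 days apart. Using the draws in Table 5:

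- Day 14 low: Day 42 at the earliest, after injection 2 (Day 28) and before injection 3 (Day 56).
- Day 28 low: Day 56, the day of injection 3.
- Day 42 low: Day 70, after injection 3.
- Day 56 low: Day 84. Day 70 or 84 low: Day 112. All precede injection 4 (Day 168).
- Day 112 low: Day 168, the day of injection 4.

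So no fall can be confirmed before injection 2, only a Day 14 low can be confirmed before injection 3, and only lows first seen by Day 84 can be confirmed before injection 4. An individual rule therefore has to hold on the first low and repeat sooner than four weeks.

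**4. Which lows need an extra draw.** After a low on Day 28, 56, 70 or 84, the next scheduled draw comes before another injection is due. After a low on Day 14, 42 or 112, the next scheduled draw is the injection visit itself, so one extra 3 ml CD4 tube is needed.

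**5. Whether a held dose stays in window.** Assume a repeat within 14 days and a result within 7. With on-time visits, a Day 14 low is repeated by Day 28 and reported by Day 35, which is the limit for injection 2 (28 + 7). A Day 42 low is reported by Day 63, the limit for injection 3 (56 + 7). If the Day 14 visit takes place on Day 21, as 6.1.1.4 allows, the result comes on 21 + 14 + 7 = Day 42, beyond Day 35.

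**6. Holds by chance.** The documents give no within-person variability, so these inputs are assumed: lognormal variation, no vaccine effect, baseline the mean of two values, seven draws before an injection (Days 14 to 112), a fall above 30% in both measures, and correlation 0.3 to 0.7. Expected holds among 60 volunteers, by simulation:

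| CV count / CD4% | Holds in 60 |
|---|---|
| 15% / 5% | 0.0 |
| 20% / 8% | 0.02 to 0.06 |
| 25% / 10% | 0.3 to 0.7 |
| 25% / 12% | at most 2.5 |

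At most about 0.1 in 60 would also be low on one repeat.

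**The case against.** The strongest reply is that the protocol already gives several ways to stop a volunteer, and this stands. An unfavorable laboratory change is an adverse event (11.2.1.1). A fall that may jeopardize the volunteer can be called an SAE (11.2.1.2), and Appendix 2 adds that "ANY clinical event deemed by the clinician to be serious or life-threatening should be considered a grade 4 adverse experience". If such an event is judged related, withdrawal from immunization is mandatory under 7.3.1.1, and one unexpected related SAE stops immunizations across the study (6.4.1 item 4). The DSMB reviews laboratory tests about every three months, can meet ad hoc, and is told of serious related events within 48 hours. A reader might infer that nothing can stop an affected volunteer; the documents do not support that. Each of these routes, however, begins with a judgment about severity, seriousness or relatedness that no CD4 value guides. The escalation review decides whether the next group opens, so it does not cover the 300 µg group.

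A second reply is that 11.5.1 also says vaccine stops for an event of any grade. Read literally, even a Grade 1 CD4 event would stop injections. That does not fit the preceding sentences, which expect discontinuation for all related grade 4 and most grade 3 events. The wording is unclear, so it cannot be relied on as a CD4 rule, but it does bar a flat statement that no stopping rule exists. Likewise, a symptom-free fall looks like Grade 1 on the generic scale, but 11.1.5 allows other criteria, so that grade is not fixed.

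A reader might want a probability that a group has one to four cases. The documents give no rate of confirmed falls, and such a figure would include cases arising after Day 168, when no injection is left to withhold. None is offered here.

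Pregnancy and intercurrent HIV infection have mandatory individual stops (6.1.1.6, 8.6), but these are yes/no diagnoses and a weak comparison for a variable count. It is also fair that holding on one unconfirmed value departs from the protocol's confirmed-decline standard, and that the word unexplained still needs an investigator's judgment.

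**Conclusion.** The concern holds in this form: the measurement named as the volunteer safeguard has no individual action threshold, and the section cited for individual action does not mention CD4. Up to 4 volunteers per group could have confirmed falls above 30% in count and CD4% with no CD4-specific rule acting. That is a ceiling set by the wording of 7.3.3, not an estimate of what will happen, and it does not mean that no one would act. It rests on 7.3.3 governing over the looser 6.4.1 item 1.

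This is a design weakness that should be fixed. It is not a fatal flaw, because discretionary routes exist and safety labs are listed for review at each injection visit after the first. What is missing is a requirement to act and consistency between volunteers.

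**What to change.** Add to 7.3.1.1 and 6.4.1:

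- An unexplained fall of more than 30% from baseline in CD4 count, together with a fall of more than 30% in CD4%, holds that volunteer's further injections.
- CD4 is repeated promptly, before the next injection is due where possible, and the medical monitor and DSMB review the case.
- If the fall is confirmed and still unexplained, injections are discontinued and safety visits continue to Week 48. If it is not confirmed, injections resume.
- Baseline is the mean of the screening and Day 0 values; 6.1.1.1 names both but not how they combine.
- A held dose does not count as a missed immunization visit under 6.1.1.4 or 7.3.1.1.

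Also correct the sentence in 11.5.1 on stopping vaccine for an event of any grade, so that it states the intended grade.

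The cost is mostly wording, since the threshold is the sponsor's own and scheduled draws are unchanged. A Day 14, 42 or 112 low needs one extra 3 ml draw. A few doses may be delayed or missed through normal variation (0 to 2.5 volunteers held in 60 under the assumed CVs), and some will fall outside the 7-day window if visits run late. The rule narrows the role of judgment but does not remove it.
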